4.2.5 Subgroup Analyses

Not applicable.

4.3 Subject Disposition

All subjects who signed the informed consent will be accounted for in Subject Disposition. The following disposition information will be summarized by the number and percentages of subjects:

- Subjects who signed the informed consent, and who comprise the Safety, Evaluable, b2M, and PP populations
- Subjects who complete the study, and who discontinued at each phase along with the reason for discontinuation

A listing of subject disposition and subjects with failed eligibility criteria will be provided.

4.4 Demographics and other Baseline Characteristics

4.4.1 Demographics

Sex, women of childbearing potential (WOCBP), age (in years), race, ethnicity, baseline BMI (kg/m²), and subjects' highest education level will be summarized by column size and blood-flow rate combinations, and Total, for the Safety population. BMI (kg/m²) will be calculated as: 10,000*weight (kg) / the square of height (cm). If height is collected in inches, it will be converted to cm by dividing the value by 2.54. If weight is collected in pounds, it will be converted to kg by dividing the value by 2.205.

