5. STUDY ENROLLMENT AND WITHDRAWAL

5.1. Inclusion Criteria

- 1. Males and females aged 40 75 years, inclusive.
- 2. ESRD requiring HD.
- 3. Dialysis vintage \geq 24 months.
- 4. Absence of clinically-relevant residual renal function.
- 5. Regular HD sessions done at blood-flow rates between 400 and 500 mL/min, and with inter-dialysis intervals of 48 hours or more.
- 6. Stable health status for at least 4 weeks prior to screening based on medical history, and findings from physical examination, laboratory tests, vital signs, and ECG, as assessed by the investigator.
- 7. Life expectancy > 6 months (as determined by the investigator).
- 8. Body mass index (BMI) between 18 and 37 kg/m², inclusive, with a minimum body weight of 52 kg.
- 9. Must be on stable doses (> 4 weeks) of all treatments for concomitant diseases (e.g., diabetes, hypertension), but this does not apply to medications for conditions related to ESRD (e.g., medications for calcium and phosphate control, anemia).
- 10. Must be able to follow the study protocol and receive the treatment in the established timeframe.
- 11. Must provide a signed and dated informed consent form.

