7.1.1.1.3. Physical Examination

A complete physical examination will be performed at screening to assess the following organ systems: skin, ENT (ears, nose, and throat), head, eyes, lungs, heart, abdomen, musculoskeletal, extremities, and neurologic and lymphatic systems. Physical examination assessments performed within 3 months of the screening visit need not be repeated. Height will be measured at screening; weight will be measured at screening and BMI calculated. Weight will be measured throughout the study both prior to and after HD.

7.1.1.1.4. 12-Lead ECG

A 12-lead ECG will be performed after the subject has rested quietly for at least 5 minutes in a supine position. In some cases, it may be appropriate to repeat abnormal ECGs to rule out technical factors contributing to ECG artifacts or abnormality. It is important that leads are placed in the same positions each time for consistency. The overall conclusion with the interpretation of the ECGs will be recorded on the appropriate CRF. The interpretation of the ECGs will be recorded as normal, abnormal but not clinically significant, or abnormal and clinically significant. QTc will be calculated using Fridericia's correction formula.

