4.8.1 Hemodialysis Parameters

Kt/V and URR (%) will be summarized for the Safety, Evaluable and PP populations, by visit and each column size/flow-rate combination.

Kt/V will be calculated with Daugirdas' formula from the pre-dialysis to post-dialysis urea nitrogen ratio (R), the weight loss (UF), session length in hours (t), and anthropometric or modeled volume (V) using the equation: $Kt/V = In (R - 0.008 \times t) + (4 - 3.5 \times R) \times 0.55 \text{ UF/V}$ (Daugirdas 1995).

URR (%) is calculated as:

URR (%) = (1 - post-dialysis BUN / pre-dialysis BUN) * 100

For evaluation of total fluid balance, the initial fluid removal goal (mL), actual fluid removal (mL), and amount differs from the goal will be summarized by column size and blood-flow rate combination.

Actual fluid removal is calculated as follows: Weight (kg) – Weight Post-Dialysis (kg) and subsequently converting weight to volume (1 kg = 1000 mL).

In addition, the number and percent of subjects who achieved the dry weight goal (i.e., Weight Post-Dialysis (kg) is less than or equal to Estimated Dry Weight) will be summarized by column size and blood-flow rate combination.

A listing of HD parameters will be provided. Other HD parameters will not be summarized but will be provided in the listing only.

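### SAP 4.4.1 converts inches to centimetres by dividing by 2.54 instead of multiplying, so baseline BMI for any height recorded in inches would be about 42 times too large

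*SAP*

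**What the plan says.** SAP 4.4.1 (Demographics) plans a table in which "baseline BMI (kg/m²), and subjects' highest education level will be summarized by column size and blood-flow rate combinations, and Total, for the Safety population". It derives BMI as 10,000 times weight in kg over the square of height in cm, and then gives two unit conversions.

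- Height: "If height is collected in inches, it will be converted to cm by dividing the value by 2.54".
- Weight: "If weight is collected in pounds, it will be converted to kg by dividing the value by 2.205".

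SAP 4.1 adds that summary tables are in general supported by a subject listing, and that departures from the planned analyses will be noted in the clinical study report.

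On collection, Protocol 7.1.1.1.3 states: "Height will be measured at screening; weight will be measured at screening and BMI calculated". It gives no unit for height. The Protocol Summary allows up to four sites, all in the US. Inclusion criterion 8 (Protocol 5.1) requires "Body mass index (BMI) between 18 and 37 kg/m², inclusive, with a minimum body weight of 52 kg".

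**The concern.** Dividing by 2.54 is the conversion from centimetres to inches, the reverse of what the sentence sets out to do. The BMI formula and the pounds rule beside it are both right, so this sentence alone is at fault. Nothing elsewhere in the SAP or protocol corrects it.

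The sentence is a derivation rule that a programmer is meant to follow, and it feeds a planned table. BMI depends on the square of height, so the height error is squared again in the result. At stake are the baseline BMI summary, by combination and in Total, and its listing. If some heights are in cm and others in inches, the mean and SD would describe nobody.

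**Working it through.** The plan states no numerical result for this rule, so there is no figure to reproduce first.

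**Inputs**

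- SAP rule for height: cm = inches / 2.54 (SAP 4.4.1).
- SAP rule for BMI: 10,000 × kg / cm² (SAP 4.4.1).
- SAP rule for weight: kg = lb / 2.205 (SAP 4.4.1). The direction is correct: 165 lb gives 165 / 2.205 = 74.8 kg.
- Eligible BMI: 18 to 37 kg/m² (Protocol 5.1).
- Planned numbers: about 15 enrolled for 12 evaluable (Protocol 10.5, SAP 3.3).
- Assumed for illustration only: the heights, weights and common BMI of 27 used below.

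**Step 1: size of the height error.** Correct height is inches × 2.54 and the SAP gives inches / 2.54. The ratio is 2.54 × 2.54 = 6.4516, so height is too small by a factor of 6.45.

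**Step 2: size of the BMI error.** BMI varies as 1/height², so it is too large by 6.4516² = 2.54⁴ = 41.62. The factor is the same for every height and weight.

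**Step 3: examples (assumed subjects).**

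| Subject | Correct height | Correct BMI | Height by SAP rule | BMI by SAP rule |
|---|---|---|---|---|
| 70 in, 80 kg | 177.8 cm | 25.3 | 27.6 cm | 1,053 |
| 67 in, 80 kg | 170.2 cm | 27.6 | 26.4 cm | 1,150 |

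For the first row: 10,000 × 80 / 177.8² = 25.3, and 10,000 × 80 / 27.56² = 1,053.

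**Step 4: against the entry range.** A true BMI of 18 would be tabulated as 18 × 41.62 = 749, and 37 as 37 × 41.62 = 1,540. Every eligible subject recorded in inches would therefore appear between about 749 and 1,540 kg/m².

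**Step 5: one inch entry among otherwise correct values.** Assume a true BMI of 27 for everyone. The affected value becomes 27 × 41.62 = 1,123.8, an excess of 1,096.8.

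- n = 12: mean = (11 × 27 + 1,123.8) / 12 = 118.4; SD = 1,096.8 / √12 = 317.
- n = 15: mean = (14 × 27 + 1,123.8) / 15 = 100.1; SD = 1,096.8 / √15 = 283.

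The true mean is 27, with an SD of 0 by construction. The same subject would distort the column for each combination that he or she entered.

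**Range.** With no heights in inches the rule never operates and nothing changes. With all heights in inches, the mean, median, minimum, maximum and SD of BMI are each 41.62 times too large.

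**The case against.** The best case on the other side is that this slip has little practical reach, and most of that stands.

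- The rule is conditional. If the case report form takes height in cm, it is never used. US sites make inches possible, but the documents do not establish that inches are used.
- BMI is not a primary or secondary endpoint (SAP 2.3, 2.4), it is not listed as a covariate in the mixed models (SAP 4.8.4, 4.8.6), and no subgroup analyses are planned (SAP 4.2.5).
- A BMI in the hundreds or above would be hard to miss at table review.

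The last argument does not remove the need for the correction. If the programmer silently multiplies, the code departs from the SAP, and SAP 4.1 says that such departures are to be noted in the study report. If the programmer follows the SAP, the table is impossible.

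A reader might also infer two stronger consequences that the documents do not support.

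- **Kt/V.** SAP 4.8.1 uses an anthropometric or a modelled volume in the Kt/V equation, so one might suppose that the wrong height carries into this secondary endpoint. That section names no formula for the volume, does not mention height and does not refer to 4.4.1. The effect would need a height-based volume, heights in inches and reuse of the demographics rule, and none of these is shown.
- **Eligibility.** One might suppose that the BMI criterion would be misapplied. BMI is calculated at the screening visit (Protocol 7.1.1.1.3 and 15.1), and nothing shows that calculation passing through the SAP's later derivation.

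**Conclusion.** The conversion in SAP 4.4.1 is wrong as written. For any height recorded in inches, derived height is too small by 6.45 and baseline BMI too large by 41.6. These factors are exact and need no assumption about the subject. Whether the error would occur depends on at least one height being recorded in inches, which is plausible but not confirmed. The effect on the mean in a mixed-unit dataset (about 118 with 12 subjects, about 100 with 15) rests on the assumed BMI of 27 and a single inch entry.

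The demonstrated consequence is confined to the baseline BMI summary, by combination and in Total for the Safety population, and its listing. The finding does not extend to Kt/V, eligibility, any other endpoint or the sample size. It is a small but definite error and worth correcting before the tables are programmed.

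**What to change.** In the height sentence of SAP 4.4.1, replace the word dividing with multiplying, so that cm = inches × 2.54. Leave the BMI formula and the pounds rule as they are. A single test value confirms the code: 70 in must return 177.8 cm.

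The cost is one word in a SAP revision. It changes nothing in the conduct of the study, the data collected, the subjects' treatment or the design. No change to SAP 4.8.1 follows from this point.

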4.4.2 Baseline Disease Characteristics

Baseline disease characteristics will be summarized by column size and blood-flow rate combinations and total for the Safety population for the following:

- Baseline Historical IDH Rate (0,1,2,3,4)
- Dialysis Vintage
- Baseline b2M Level

4.4.3 Medical History

Medical history will be coded by system organ class (SOC) and preferred terms (PT) using the Medical Dictionary for Regulatory Activities (MedDRA) version 23.0. A listing of medical history data will be provided.

4.4.4 Serology

Serology, including hepatitis B surface/core antigen (HBsAg), hepatitis C antibody (HCV Ab), and human immunodeficiency virus antibody (HIV Ab, HIV1/HIV-2), will be collected at Visit 1. Serology will not be summarized but will be provided as a listing.

4.5 Protocol Deviations

Protocol deviations will be summarized by column size and blood-flow rate combinations with each deviation category broken down into major and minor for the Safety population.

4.6 Methods for Handling Missing Data

No imputation of missing data will be performed.

4.7 Primary Analyses

Primary analyses will evaluate safety and tolerability of the column at blood-flow rates greater than 250 mL/min in subjects with ESRD undergoing HD. Except where indicated, primary endpoints will be summarized by each column size and blood-flow rate combination (S-15 250 mL/min, S-15 up to 450 mL/min, S-25 250 mL/min, S-25 up to 450 mL/min, S-35 up to 450 mL/min) and total using both Safety and Evaluable populations.

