Renal Disease Undergoing Hemodialysis

Objective: The objective of this study is to evaluate the safety and tolerability of the

column at blood-flow rates greater than 250 mL/min in subjects with end-stage renal disease (ESRD) undergoing hemodialysis (HD). The study will assess the safety, tolerability, and impact on HD parameters when the

column is used at a blood-flow of up to 450 mL/min.

Précis: This is an open-label study in 12 to 15 subjects between 40 and 75 years of age with ESRD on HD. The purpose of the study is to compare the safety and tolerability of two blood-flow rates when the b2M column is used during HD. The column was originally developed for blood-flow rates of 250 mL/min, and in this study it will be evaluated at both 250 mL/min

and up to 450 mL/min.

After screening (Visit 1), subjects will undergo HD at a lower blood-flow rate (250 mL/min) for a 1-week run-in period to determine the HD duration required to achieve adequate fractional urea clearance (Kt/V) (> 1.2). Daugirdas' formula will be used to calculate Kt/V (Daugirdas 1993, Daugirdas 1995, Daugirdas and Schneditz 1995).

The column comes in 3 sizes (S-15, S-25, S-35) and each size will be tested at blood-flow rates of 250 mL/min and up to 450 mL/min as tolerated (see Appendix 17.1: Escalation, De-escalation, and Discontinuation Rules for Treatment with the Column). Each column-size and blood-flow rate combination will be evaluated during 3 consecutive HD sessions before proceeding with the next combination, as follows:

- Week -1 (Visits 2-4) HD run-in period (no column) at 250 mL/min to determine Kt/V
- Week 1 (Visits 5-7) column S-15 at 250 mL/min
- Week 2 (Visits 8-10) column S-15 at up to 450 mL/min
- Week 3 (Visits 11-13) column S-25 at 250 mL/min
- Week 4 (Visits 14-16) column S-25 at up to 450 mL/min
- Week 5 (Visits 17-19) column S-35 at 250 mL/min
- Week 6 (Visits 20-22) column S-35 at up to 450 mL/min
- Week 7 (Visit 23) End of study (EOS), no column, HD at patient's standard rate

The first treatment with the column S-15 (150 mL) will occur midweek (e.g., on Wednesday for subjects on a Monday/Wednesday/Friday schedule and on Thursday for subjects on a Tuesday/Thursday/Saturday schedule).

The escalation to the subsequent column-size and flow-rate combination will occur mid-week (e.g., on Wednesday for subjects on a Monday/Wednesday/Friday schedule and on Thursday for subjects on a Tuesday/Thursday/Saturday schedule).

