The duration of each HD treatment will be adjusted to ensure adequate Kt/V with a reduced flow rate (approximately 4-6 hours at 250 mL/min, 3-4 hours at up to 450 mL/min). During each week determination of HD adequacy will include KtV > 1.2 (calculated from measurements of blood urea) and urea reduction ratio (URR) (weekly URR > 65%).

The most important known potential risk for use of the column is an increased risk of IDH. Risk mitigations may include prophylactic administration of saline, supine positioning/lower limb elevation, avoidance of fasting before HD, avoidance of food intake during HD, use of cooled dialysate, education about the importance of avoiding excessive fluid gain between HD sessions (interdialytic weight gain), and avoiding the use of ultrafiltration rates (UFR) above 13 mL/kg/h. Concomitant medications, especially medications related to or affecting blood pressure (BP), should remain stable while on study and receiving HD with the

The occurrence of IDH events during each week, as outlined in Appendix 17.1: Escalation, De-escalation, and Discontinuation Rules for Treatment with the Column, will be one factor used to determine column size/blood-flow rate escalation/de-escalation as well as discontinuation from the study. There is also a possibility that the blood-flow rate of 450 mL/min cannot be attained due to factors related to the dialysis circuit or other technical issues. If the blood-flow rate of 450 mL/min cannot be attained, it can be adjusted down to enable continued dialysis at a blood-flow rate as high as possible. The reason(s) for the inability to attain a blood-flow rate of 450 mL/min must be documented.

Endpoints:

Primary Endpoints:

- Safety and tolerability of each column size at each blood-flow rate.
 - Evaluation of safety and tolerability will include assessment of the rate and severity of all adverse events (AEs), with analyses of adverse device effects (ADEs), treatment-emergent AEs (TEAEs), number of IDH events, and changes in total and free hemoglobin (Hgb).
 - Tolerability will be assessed by the proportion of subjects who can escalate to and tolerate each column size and blood-flow-rate combination.

Secondary Endpoints

- Weekly Kt/V and URR.
- Total fluid balance for each column-size flow-rate combination.
- Proportion of subjects who are able to achieve the dry weight goal during the allotted HD duration for each column size and flow rate combination.

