4.2. Study Endpoints

4.2.1. Primary Endpoints

- Safety and tolerability of each column size and each blood-flow rate.
 - Evaluation of safety and tolerability will include assessment of the rate and severity of all AEs, with analyses of ADEs, TEAEs, number of IDH events, and changes in total and free Hgb.
 - O Tolerability will be assessed by the proportion of subjects who can escalate to and tolerate each column size and blood-flow-rate combination.

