17.1.2. De-escalation Rules

The purpose of the de-escalation rules is to ensure the safety of a subject who is experiencing IDH, anemia or other safety issues that may be related to the column size.

A subject should be de-escalated if during the 1-week treatment period they experience the number of IDH events described in the table above and/or have an Hgb level < 9 g/dL despite receiving optimized treatment with ESA.

De-escalation will only be applicable at V11 through V19 as shown in Figure 4 below. Subjects who do not tolerate treatment with the S-15 column at any time prior to V11 or after V19 will be discontinued (see Section 17.1.13. Discontinuation Rules).

Figure 4. De-escalation Schematic

Subjects will continue with the same visit schedule after de-escalation. At the visit following confirmation of de-escalation, treatment will resume with the previous column size at the high flow rate (up to 450 mL/min).

- ➤ If de-escalation occurs during V11 through V16, subjects will resume treatment at the next scheduled visit with the S-15 column at up to 450 mL/min and will continue with this column size/flow rate combination through EOT (V22).
- ➤ If de-escalation occurs during V17 through V19, subjects will resume treatment at the next scheduled visit with the S-25 column at up to 450 mL/min and will continue with this column size/flow rate combination through EOT (V22).

Table 4 below illustrates the visit schedule for subjects who de-escalate. *Note*: the only change compared to Section 15 is column size and flow rate.

Table 4. Schedule of Events for Subjects Who De-escalate

					,	Treatm	ent Peri	iod					EOS
Visit Number	V11	V12	V13	V14	V15	V16	V17	V18	V19	V20	V21	V22 (EOT)	V23
Study Week		Week 3			Week 4	ļ	,	Week 5			Week	6	Week 7
Study Day(s) (± 1)	Day 15	Day 17	Day 20	Day 22	Day 24	Day 27	Day 29	Day 31	Day 34	Day 36	Day 38	Day 41	Day 43
Procedure													
Physical examination													X
12-lead ECG													X
Targeted physical examination	X	X	X	X	X	X	X	X	X	X	X	X	
Weight	X	X	X	X	X	X	X	X	X	X	X	X	X
Vital signs ¹	X	X	X	X	X	X	X	X	X	X	X	X	X
Laboratory tests ²		X	X		X	X	X	X	X	X		X	X
Column size			S-	15			S-15	OR S-2	.5 (if de	e-escala	ated aft	er V16)	
Hemodialysis blood-flow rate (mL/min)						Up	to 450						
Assessment of fluid status	X	X	X	X	X	X	X	X	X	X	X	X	
Kt/V assessment		X			X		_	X			X	X	_
Adverse events and concomitant medications	X	X	X	X	X	X	X	X	X	X	X	X	X

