4.8 Secondary Analyses

Secondary analyses include HD parameters, thrombosis events, weight, b2M, complement factors, and other plasma protein levels. Except where indicated, secondary endpoints will be summarized by each column size and blood-flow rate combination (S-15 250mL/min, S-15 up to 450 mL/min, S-25 250mL/min, S-25 up to 450 mL/min, S-35 250mL/min, S-35 up to 450 mL/min) using both Safety and Evaluable populations.

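### SAP 4.7 lists five of the six column-size/flow-rate combinations for the primary endpoints and omits S-35 at 250 mL/min, probably a drafting slip

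*SAP*

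**What the plan says.** The protocol's primary endpoint covers every size at every rate: "Safety and tolerability of each column size at each blood-flow rate" (Protocol Summary). Protocol 4.2.1 adds: "Tolerability will be assessed by the proportion of subjects who can escalate to and tolerate each column size and blood-flow-rate combination". The Protocol Summary schedules six treatment weeks, one per combination, and the fifth is "Week 5 (Visits 17-19) column S-35 at 250 mL/min". SAP 3.1 and 3.6 carry the same six.

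SAP 4.7 opens with a general rule: "Except where indicated, primary endpoints will be summarized by each column size and blood-flow rate combination". It then gives a bracketed list. The first two entries are S-15 at 250 and S-15 at up to 450 mL/min, and the rest reads "S-25 250 mL/min, S-25 up to 450 mL/min, S-35 up to 450 mL/min) and total using both Safety and Evaluable populations". No entry for S-35 at 250 mL/min appears, and no reason is given.

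SAP 4.8, for the secondary endpoints, ends its list with "S-25 up to 450 mL/min, S-35 250mL/min, S-35 up to 450 mL/min) using both Safety and Evaluable populations". All six combinations are there.

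On movement between columns, Protocol 17.1.2 states: "De-escalation will only be applicable at V11 through V19". Protocol 17.1.3 discontinues a subject who does not tolerate S-35 at the higher rate. SAP 4.1 keeps a de-escalating subject in the analysis only until the de-escalation. It also plans to assess the effect of flow rate within a given column size.

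**The concern.** SAP 4.7 is the only place that enumerates the groups for the primary endpoints, so someone building tables could reasonably take its list as the specification. The missing entry is the week in which subjects first meet the largest column.

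If the list were followed, the primary summaries by combination would show S-35 only at up to 450 mL/min, that is, only in subjects who had already got through Week 5. A subject who de-escalates in Week 5 contributes S-35 data in that week and nowhere else. The within-S-35 comparison of 250 with up to 450 mL/min, which bears directly on the study's purpose, would have only one of its two sides in the primary tables.

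**Working it through.** **The plan's own figure.** SAP 3.3 gives about a 70% probability of at least one IDH event in each week, that is, for each combination, with 12 subjects and an assumed rate of 10%. The check is 1 − (1 − 0.10)^12 = 1 − 0.9^12 = 0.718. The figure reproduces. It is stated per combination, so it presumes that each of the six weeks is looked at separately.

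**Counting the combinations.**

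| Source | S-15 250 | S-15 ≤450 | S-25 250 | S-25 ≤450 | S-35 250 | S-35 ≤450 | Count |
|---|---|---|---|---|---|---|---|
| Design (Protocol Summary; SAP 3.1, 3.6) | yes | yes | yes | yes | yes | yes | 6 |
| SAP 4.8 list (secondary) | yes | yes | yes | yes | yes | yes | 6 |
| SAP 4.7 list (primary) | yes | yes | yes | yes | **no** | yes | 5 |

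3 sizes × 2 rates = 6. The single difference is S-35 at 250 mL/min.

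**Where de-escalation from S-35 can happen.**
- S-35 is used at V17-V22: V17-V19 at 250 mL/min and V20-V22 at up to 450 mL/min.
- De-escalation is possible at V11-V19 (Protocol 17.1.2).
- The overlap is V17-V19, all at 250 mL/min.
- From V20 on, intolerance of S-35 leads to discontinuation (Protocol 17.1.3).

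Every de-escalation from S-35 therefore arises in the unlisted combination. SAP 4.7.4 makes de-escalation by reason part of the primary tolerability summary.

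**Size of the unlisted cell.** Assume 12 subjects complete all visits, with three sessions a week:
- all six combinations: 12 × 3 × 6 = 216 sessions;
- the five listed: 12 × 3 × 5 = 180 sessions;
- difference: 36 sessions, and 36/216 = 16.7%.

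This measures how much data the cell could hold. It does not measure any bias.

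**Hemoglobin.** As the laboratory table in Protocol 15.3 reads, on-column total and plasma-free hemoglobin are drawn at V6, V9, V18 and V21. V18 falls in Week 5, so the unlisted combination holds one of those four time points. The table was read from PDF, so the visit columns should be confirmed against the source.

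**The case against.** The best reply is that nothing was decided here. The sentence holding the list says each combination, and SAP 4.7.3 and 4.7.4 repeat each without a list. SAP 4.7.2 also groups by combination without restricting it. A bracket with one item missing does not outweigh all that, and a careful programmer would restore the sixth column. I accept that this is probably a slip and not a chosen analysis. It remains a contradiction inside the section that governs the primary tables, and it should not be left to the programmer to resolve.

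Several stronger conclusions are tempting, and the documents do not support them.

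- *Week 5 is lost from all primary output.* The shells are separate files and have not been seen. SAP 4.1 promises listings of all data, with the combination shown where applicable. Protocol 10.4.2 counts subjects completing a column size at both rates, which needs Week 5.
- *S-35 de-escalations would be visible only in the total.* The plan does not say how the total is formed. Under the literal list they might be in it or not.
- *The omission makes the S-35 up-to-450 group show no de-escalations.* That zero follows from the V11-V19 window and would remain after the correction. Failures in Week 6 are counted as discontinuations in SAP 4.7.4.
- *Attrition on S-35 would be hidden.* SAP 4.7.4 reports the number entering each combination. Even with five columns, a fall between S-25 and S-35 at up to 450 mL/min would show. Its timing and cause would not.

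The study is also descriptive (SAP 3.2), so no hypothesis test on a primary endpoint is at stake.

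**Conclusion.** The inconsistency is certain: SAP 4.7 names five combinations where the design, the primary endpoint and SAP 4.8 require six. Its consequence is conditional. It arises only if the list is applied as written to summaries presented by combination. In that case IDH, hemoglobin and tolerability have no separate column for S-35 at 250 mL/min, the only combination from which S-35 de-escalation can occur, and the flow-rate comparison within S-35 has no reference. The cell is one of six combinations, or 16.7% of column sessions if everyone completes. The sample size and the 70% figure do not change. The point warrants correction before the tables are run because it concerns the primary endpoints. It is not evidence that the sponsor meant to exclude Week 5.

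**What to change.** In SAP 4.7, insert S-35 250 mL/min before S-35 up to 450 mL/min so that the list matches SAP 4.8. Then check that the shells for 4.7.1 to 4.7.4 carry all six combinations wherever results are shown by combination. No separate request for a Week 5 denominator is needed, because SAP 4.7.4 already reports the number entering each combination and will include Week 5 once the list is right.

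The cost is one phrase in the SAP and, if the shells were built from the short list, one column in the affected tables. No data collection, sample size or clinical rule is touched.
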